## 4. Statistical analysis

First, data will be summarized according to its type. Categorical data will be summarized using frequency and percentage. Continuous data will be tested for normality. if the data is normally distributed, we will summarize it using mean and SD, and if not, median and IQR will be used. We will assess the difference between the population according to their sociodemographic data using a Chi-square and a Mann-Whitney U test. A p-value of <0.05 will be used as a cutoff point for statistically significant results. We will assess the correlation between all continuous data (internet addiction, gaming, porn addiction, stress, depression, and anxiety levels). Finally, a multiple linear regression test will be used to assess the relationship between the assessed variables.

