### Introduction

Internet usage has increased greatly. It is expected to be more than 4 billion by the end of this year(1). About 80% of them spend most of their internet time on social media, and are expected by 2026 to be about 50% of the total population to use social media at least once a month(1). The internet is mainly used to connect with friends, relatives, learn new skills, or for entertainment, such as video gaming (2). However, with this increasing usage, internet addiction can easily increase.

Internet addiction or pathological internet use is defined as uncontrolled, excessive use of it, with uncontrolled time consuming that can cause distress, and impairment (3,4). The prevalence of internet addiction varied between regions. A study in the seven countries in Europe reported a prevalence of addiction among adolescents to be 1%, and an additional 12.7% at risk of having addiction(5). In Turkey, a recent cross-sectional study conducted by Sayili et al found a prevalence of 18.3% (6). In the Middle East, the prevalence varied greatly from 0.9% to 33% among adolescents (7–9). For Egypt, Ibrahim et al, 2020 assess the prevalence of internet addiction among undergraduate medical students in Assiut University. They collected data from 321 students, revealing a prevalence being 9%. They also found a statistical association between internet addiction and increasing depression among these students(10). Sayed et al, 2022 was another cross-sectional study that was conducted among pharmacy students in Egypt. They also found a prevalence being 38.5%. They also found a statistically significant association between internet addiction and stress, depression and anxiety.(11)

Additionally, internet video gaming is another addictive problem that can affect adolescents. A previous meta-analysis showed that gaming addiction prevalence ranged from 0.9% to 19.9%, with males being higher than females(12). Also, Pitanupong et al 2025 showed a prevalence of about 8.4% among Thailand medical students. (13). Shouman et al 2023 was a cross-sectional study conducted among university students in Egypt at Mansoura university. They found a 6% prevalence among these students. Again,

they found a statistically significant association between gaming addiction and psychological factors. (14)

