#### Rational

Medical students, in particular, use the internet frequently. They use it in training, faculty assignments, research projects, and so on, which can make them depend greatly on the internet. This potentially can increase their addiction to the internet, subsequently increasing their addiction to video gaming and porn addiction. (19). In the Middle East, few studies have tried to assess the prevalence of internet addiction and its association with increased depression, anxiety, and stress(7,9,18) among medical students. Despite that, there is a lack of studies on gaming addiction and porn addiction.

We aim to assess the prevalence of internet addiction alongside video gaming and porn addiction among medical students and interns in the Middle East (MENA region). We also aim to assess the relationship of these three addictive behaviors with each other and their relationship with increased stress, anxiety, and depression among this population.

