#### 3. Data collection method

An online questionnaire will be shared via social media platforms such as Facebook, WhatsApp, and Telegram.

The questionnaire is composed of 8 sections as follows:

- The first section provides a brief introduction to the topic, its importance in the research field, and consent to participate in the study.
- ➤ In the second section, sociodemographic data will be collected, such as age, gender, type of university, smoking level, number of sleeping hours, difficulty in accessing the internet, and reason for using internet platforms
- In the third section, we will ask about internet addiction. We will use the Internet Addiction Scale (IAT) (21,22) This scale is a 20-question Likert scale, and each question has six answer scales from 0 to 5 (Not applicable, rarely, occasionally, frequently, often, and always). This makes a range of scores from 0 to 100.

- The participants can be classified into normal usage, mild, moderate, and severe levels of addiction if they score (0-30), (31-49), (50-79), and (80-100), respectively.
- ➤ In the fourth section, Gaming addiction will be assessed. We will use the Internet Gaming Disorder Scale—Short-Form (IGDS9-SF) (23,24)

  This scale consists of a 9-question Likert Scale. Each question has five answers, scored from 1 to 5. Total score ranges from 9 to 45, with a higher score indicating a higher level of gaming disorder.
- ➤ We used the GAD-7 scale (25,26) in the fifth section to assess the level of anxiety. This scale consists of a 7-question Likert scale, each one has four answers scored from 0-3, making a range of scores from 0-21.

  Students can be classified into minimal, mild, moderate, and severe levels of anxiety if they score (0-4), (5-9), (10-14), and (15-21), respectively.
- ➤ In the sixth section, we used the Patient Health Questionnaire-9 (PHQ-9) (26,27)to assess the level of depression.
   A 9-question Likert scale with four answers for each question. Scores range from 0-3, making the range of scores from 0-27.
   Students can be classified into minimal, mild, moderate, moderately severe,
  - and severe levels of depression if they score (0-4), (5-9), (10-14), (15-19), and (20-27), respectively.
- ➤ In the seventh section, we asked about stress level through the Perceived Stress Scale-10 (PSS-10) (Ali et al., 2021; Cohen et al., 1983). A 10-question Likert Scale, and each question has 5 answers, which score from 0-4. A total score ranges from 0-40.

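### Does naming only Chi-square and Mann-Whitney U leave score comparisons across three or more groups without a valid test?

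*Protocol*

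**What the plan says.** The Statistical analysis section is one paragraph. For group differences it says "We will assess the difference between the population according to their sociodemographic data using a Chi-square and a Mann-Whitney U test", and its significance threshold is "A p-value of <0.05 will be used as a cutoff point for statistically significant results". The normality check in the same paragraph decides only the summary statistics, not the test. The paragraph then plans correlations, treating as continuous "all continuous data (internet addiction, gaming, porn addiction, stress, depression, and anxiety levels", and closes with a multiple linear regression relating the assessed variables, without naming outcomes or predictors.

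The factors are listed in 3. Data collection method: "such as age, gender, type of university, smoking level, number of sleeping hours, difficulty in accessing the internet, and reason for using internet platforms". No response categories are given for any of them.

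The same section gives severity bands for the IAT, GAD-7, PHQ-9 and PSS-10 and a cut-off of 76 for the PPCS. For the gaming scale (IGDS9-SF) it gives only the total: "Total score ranges from 9 to 45, with a higher score indicating a higher level of gaming disorder".

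**The concern.** Mann-Whitney U is a two-sample test. The protocol names neither Kruskal-Wallis nor analysis of variance, nor any other test for several groups. Some listed factors plausibly have more than two categories. Smoking level sounds graded. Several reasons for internet use appear in the background text: "The internet is mainly used to connect with friends, relatives, learn new skills, or for entertainment, such as video gaming" in the Introduction and, for medical students, "They use it in training, faculty assignments, research projects, and so on" in the Rational.

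Five scales can be compared across such a factor by Chi-square on their bands or cut-off. The gaming scale has neither, so its total seems to have no fitting named test. Read as a closed list, the sentence leaves three options: collapse the factor to two levels, drop the comparison, or run Mann-Whitney pair by pair. Collapsing can hide a real difference, and unadjusted pairwise testing inflates false positives.

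**Working it through.** **The plan's own figure.** Inputs from 7. Sampling: prevalence 50%, margin 5%, 95% confidence, 10% nonresponse.
- n = 1.96² × 0.5 × 0.5 / 0.05² = 384.1. The stated 383 agrees with a finite-population correction: an assumed population of 100,000 to 200,000 gives 382.7 to 383.4.
- 383 × 1.10 = 421.3, rounded up to 422. Over the 11 countries, 422 × 11 = 4642, as stated.
- Respondents before the nonresponse allowance: 383 per country, 383 × 11 = 4213 pooled.

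**Assumptions, none from the protocol.** 3 to 5 equal levels per factor; one level shifted by 0.3 SD; two-sided 0.05; for simulations, a right-skewed integer score from 9 to 45.

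**If pairs were tested without adjustment.** The number of pairs is k(k−1)/2. The chance of at least one false positive with equal groups is the probability that a studentized range exceeds 1.96 × √2. Simulation: total n = 383, 4,000 runs.

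| Levels | Pairs | Theory | Simulated pairwise | Simulated Kruskal-Wallis |
|---|---|---|---|---|
| 3 | 3 | 12.2% | 12.0% | 5.1% |
| 4 | 6 | 20.3% | 19.4% | 5.0% |
| 5 | 10 | 28.6% | 28.8% | 5.7% |

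**If three levels were collapsed to two, one country.** Three levels of 127 (383/3, rounded down), one shifted by 0.3 SD; simulated power over 3,000 runs:
- shifted level kept apart: 76%
- shifted level merged with another: 26%
- Kruskal-Wallis on all three: 67%

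**The same collapse, pooled.** 4213/3 is about 1404 per level. Merging the shifted level with an unshifted one halves the contrast to 0.15 SD, comparing 2808 with 1404:
- z = 0.15 / √(1/1404 + 1/2808) = 0.15 / 0.0327 = 4.6, or about 4.5 allowing for the efficiency of Mann-Whitney.
- Power ≈ Φ(4.5 − 1.96) = Φ(2.54), about 99%.

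The loss from collapsing therefore nearly vanishes at this effect size in the pooled sample. The inflation from unadjusted pairwise testing does not depend on sample size, but the protocol does not plan such testing.

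**What the named methods cover.**
- Two-level factor, any score: Mann-Whitney U.
- Factor with any number of levels, outcome with bands or a cut-off: Chi-square.
- Multi-level factor, continuous score: neither named test; the planned linear regression can carry it with indicator variables.
- Reason for use, if respondents may tick several: each reason is yes/no, and Mann-Whitney U fits.
- Gaming scale: the first objective asks for the prevalence of gaming addiction, so participants must be classified. Once they are, Chi-square applies to this scale too. The absent cut-off is a separate question.

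**The case for a change.** The strongest case for a change is that the protocol does not leave the choice open. It names tests for this comparison, and the pair does not cover an ordinary multi-category factor. A later analysis plan would have to extend the stated method, not just add detail. Regression is listed separately and is not assigned to sociodemographic differences. Choosing how to collapse a factor after seeing the data is a real freedom: in the one-country example it moves power from 76% to 26%. A few sentences would close it, at no cost in data or sample size.

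Part of this stands. No test for three or more groups is named, and adding Kruskal-Wallis with adjusted follow-up would be a harmless completion of the wording. But calling the list closed is an inference; the sentence does not say so, and each named test is right for its own use. Whether any single-response factor has three or more levels is also inferred, partly from background prose and not from response options. The 11 countries do not settle it: country is not among the listed sociodemographic items, and no objective compares countries.

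**Conclusion.** No change is needed. A test for three or more groups is a routine detail that a one-paragraph outline can leave to the analysis plan, and a competent analyst would supply it. Used where they fit, the named tests give valid results.

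The calculated harm (12% to 29% false positives, or power down to 26%) assumes 3 to 5 equal levels, a 0.3 SD shift for the power figures, and either unadjusted pairwise testing or an unfavourable merging of levels, neither of which the protocol states. The low power also assumes analysis within one country, which the section does not describe; pooled, it is about 99%.

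The three objectives concern prevalence of the addictions, prevalence of anxiety, depression and stress, and the relation between the two sets. The prevalence, correlation and regression results behind them do not depend on this comparison. The conclusion would be weaker if the authors meant the two tests as an exhaustive list and the questionnaire has single-response factors with three or more levels; even then the matter would be minor.

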# Methodology

# **Technical Design**

- 1. Study design: Cross-sectional study
- 2. **Setting**: Medical students in some Middle East countries (Egypt, Sudan, Somalia, Libya, Morocco, United Arab Emirates, Jordan, Syria, Yemen, Iraq, and Palestine)
- 3. **Time**: From July 2025 to December 2025
- 4. **Population**: Arabic Medical students in the MEAN region

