### 7. Sampling

We calculated the total sample size using Epi Info version 7.2.60(*Epi InfoTM* | *CDC*, n.d.) Assuming a 50% prevalence rate and a 5% error margin with a 95% confidence interval, the sample size required for each country is 383. After adding a 10% nonresponse rate, the final sample size is about 422 for each country, so the total sample size will be 4642

8. Sampling Technique: Convenience Sampling

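### The sample is set country by country, but the named tests, correlations and regression carry no country term, so differences between countries can appear as, or mask, associations between students

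*Protocol*

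**What the plan says.** Technical Design lists 11 countries: "Egypt, Sudan, Somalia, Libya, Morocco, United Arab Emirates, Jordan, Syria, Yemen, Iraq, and Palestine". Section 7 (Sampling) sizes each one separately: "Assuming a 50% prevalence rate and a 5% error margin with a 95% confidence interval, the sample size required for each country is 383". It continues: "After adding a 10% nonresponse rate, the final sample size is about 422 for each country, so the total sample size will be 4642". Recruitment is by convenience (section 8), and Operational design adds a pilot in each country.

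The population and objectives, by contrast, are regional. Technical Design defines the population as "Arabic Medical students in the MEAN region", and the Objective section asks about the region as a whole.

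Operational design, section 4 (Statistical analysis), fixes the association analyses:
- group comparisons: "We will assess the difference between the population according to their sociodemographic data using a Chi-square and a Mann-Whitney U test";
- score-to-score relations: "We will assess the correlation between all continuous data", covering internet, gaming and pornography addiction, stress, depression and anxiety;
- a closing multiple linear regression, with no covariates listed.

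The significance cut-off is p < 0.05. No stratification by country, adjustment for country or within-country analysis is mentioned. Country is also absent from the sociodemographic items in the Data collection section, though that list is given only as examples.

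**The concern.** Country is the unit by which the sample is built, yet the ordinary Chi-square, Mann-Whitney U and simple correlation have no place for a stratum. Suppose countries differ both in a student characteristic (type of university, smoking, internet access) and in a score. The combined data then show an association even if students within each country show none. If country effects run in opposite directions, a real within-country association can be weakened or hidden.

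The protocol gives a reason to expect country effects that move several scores together. The Data collection section offers Arabic and English questionnaires because the language of medical teaching differs between countries. Questionnaire language will therefore probably track country, and a language-related shift in responding could affect several scales at once. That is the case in which the error is largest.

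At stake are the third objective (relations between the addictions and depression, anxiety and stress) and every sociodemographic comparison. A regional prevalence estimate raises separate questions that are not part of this point.

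**Working it through.** **1. The plan's own figures.** With prevalence 0.50, margin 0.05 and 95% confidence, n = 1.96² × 0.25 / 0.05² = 384.1. A finite-population correction for 100,000 students gives 382.7, so the stated 383 is reproduced within tolerance. Then 383 × 1.10 = 421.3, rounded up to 422, and 422 × 11 = 4642. The arithmetic confirms that the country is the sizing unit.

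**2. How small a correlation becomes significant.** At N = 4642 and two-sided 0.05 (the protocol does not state sidedness), the threshold is about 1.96/√4642 = 0.029. At 383 × 11 = 4213 it is 0.030.

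**3. Inputs for the error rate.** From the protocol: 11 countries, 422 students each, alpha 0.05. Assumed, because the protocol gives no value:
- the share of score variance lying between countries (ICC, equal for both variables): 0.01 to 0.10;
- the correlation of country effects across the two variables: 0 or 0.8.

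The true within-country association is set to zero.

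**4. Simulation.** There were 2000 runs per setting for correlations and 600 for Mann-Whitney (second variable split at zero). Entries are the percentage of runs significant at 0.05.

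| ICC | Pooled correlation, independent country effects | Pooled correlation, effects correlated 0.8 | Pooled Mann-Whitney, independent | Pooled Mann-Whitney, correlated 0.8 |
|---|---|---|---|---|
| 0.01 | 5.6 | 8.7 | 5.2 | 6.2 |
| 0.02 | 6.8 | 19.4 | 6.8 | 16.5 |
| 0.05 | 15.8 | 60.5 | 11.7 | 45.8 |
| 0.10 | 35.5 | 89.0 | 27.0 | 82.3 |

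The same correlation on country-centred scores is significant in 4.6% to 5.6% of runs in every setting. A separate set of 1000 runs with both variables dichotomised and independent country effects gave pooled Chi-square rates of 6.5%, 6.5%, 9.3% and 19.1% at the four ICC values.

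**5. Check by formula.** Let ρ be the correlation of country effects. The pooled r is then roughly normal with mean ρ × ICC × 10/11. Its variance is ICC² × 10(1 + ρ²)/11² + 1/4642.
- ICC 0.05, ρ = 0: the standard deviation is √(0.01437² + 0.01468²) = 0.0205. The chance that |r| exceeds 0.0288 is 16.1% (simulated 15.8%).
- ICC 0.10, ρ = 0.8: the mean is 0.8 × 0.10 × 10/11 = 0.073, the standard deviation 0.0396, and the chance 87.2% (simulated 89.0%).

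**6. Size of the false correlation.** The mean r is 0.036 at ICC 0.05 and 0.072 at ICC 0.10 with effects correlated 0.8, and about zero with independent effects. Across all settings the 95th percentile of |r| runs from 0.029 to 0.137. By symmetry, country effects correlated -0.8 shift r downward by the same amount, which is how a real association could be masked.

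**The case against.** Three objections carry weight.

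- **Pooling is not stated.** The word does not appear, and a per-country sample size leaves within-country analysis possible. This stands as a limit on the wording. Even so, the population and objectives are regional and no within-country analysis is named, so one combined analysis is the natural reading.
- **The regression can take country, and its covariates may be left to an analysis plan that is not shown.** The second part is fair, and an unlisted covariate is not itself the defect. But the protocol also fixes other tests by name, and a regression that might include country would not correct them. They need stratifying or replacing.
- **The effect may be negligible.** It needs both variables to differ between countries. At ICC 0.01 to 0.02 with independent country effects, the error rate is 5.6% to 6.8%, close to nominal. This stands too.

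A reader might go further and take the Introduction as proof of large differences between the study countries, and so conclude that pooled results will be spurious. The documents do not support that. The 9% and 38.5% both come from Egypt (medical and pharmacy students), and the 18.3% is from Turkey, which is not a study country. The 0.9% to 33% range is described as among adolescents, and one of the three references behind it is from Bangladesh. None of these measures variation between study countries among medical students. Nor does the protocol describe separate national recruitment: it gives a target and a pilot per country, with a questionnaire shared on social media.

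**Conclusion.** The point holds as a risk and is not a demonstrated bias. The design is organised by country, the named association analyses are not, and followed as written they leave associations open to confounding by country. Whether this matters depends on a between-country variance that the protocol does not give. The false-positive rate for a pooled correlation runs from about 6% (ICC 0.01, independent country effects) to about 89% (ICC 0.10, effects correlated 0.8), against about 5% after centring on country.

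The simulated false correlations are small, so for the score-to-score relations the harm is mainly false significance at N = 4642, with little distortion of the estimate. These figures assume equal country sizes, normal scores and the same ICC for both variables. Convenience sampling may not deliver equal sizes. The change is worth making because it costs little and uses a structure the design already has.

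**What to change.** Record country of study for every respondent; checking the per-country target needs this in any case. In section 4, state that the primary association analyses are stratified by or adjusted for country, for example:

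- Cochran-Mantel-Haenszel tests in place of the plain Chi-square;
- van Elteren tests in place of the plain Mann-Whitney U;
- rank correlations on country-centred scores;
- country as a fixed effect in the linear regression.

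Other methods that condition on country would serve equally well. Show the unstratified results as a supplement, so that readers can see how far country accounts for them. The cost is a change of wording and slightly more analysis work with standard software. No further participants are needed, and the only data item required is country of study.

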On the other hand, overuse of the internet can lead to an increase in problematic pornography use. Karim et al. 2025(15) found a significant association between increased usage of the internet and pornography addiction (P value: <0.001). Additionally, previous studies showed a prevalence of porn addiction ranging from 3.2% to 16.6%(16). Also, a negative correlation between education level and porn addiction was observed.(17).

All these behavioral addictions increase depression, anxiety, and stress for addicts. Several cross-sectional studies have assessed the positive correlation between either internet, gaming, or porn addiction, and an increase in anxiety and depression. (6,10,13,15,18) However, to our knowledge, no single study has assessed these three addictive behaviors together with depression, anxiety, and stress in Arab countries.

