## **Objective**

- 1. To assess the prevalence of internet, gaming, and porn addiction among Medical students and interns in the MENA region
- 2. To assess the prevalence of anxiety, depression, and stress among this population.
- 3. To assess the relation between these addictions and depression, anxiety, and stress.

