  - Students can be classified into mild, moderate, and severe levels of stress if they score (0-13), (14-26), and (27-40), respectively.
- Finally, the eighth section will ask about porn addiction. The Problematic Pornography Consumption Scale (PPCS) (29) will be used, which consists of an 18-question Likert Scale. Each question consists of 7 answers, and

their scores range from 1-7. A total score ranges from 18-126, with higher levels indicating a higher level of porn addiction. A 76 score will be used as a cut-off value to indicate a high risk of porn addiction.

We used the Arabic version alongside the English version of the validated questionnaire because some Arabic countries did not teach medicine in English so the English will be a challenge for them.

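### If gaming and pornography scores pile up at their minimum, default regression standard errors for their slopes would be modestly too small; one clause specifying robust (HC3) errors removes the risk

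*Protocol*

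**What the plan says.** Objective 3 of the protocol is "To assess the relation between these addictions and depression, anxiety, and stress". Under Operational design, 4. Statistical analysis, the method is brief: "We will assess the correlation between all continuous data (internet addiction, gaming, porn addiction, stress, depression, and anxiety levels"), and then "a multiple linear regression test will be used" to relate these variables to one another. The decision rule is "A p-value of <0.05 will be used as a cutoff point for statistically significant results". The section does not name the outcome or the predictors, does not give the type of standard error, and promises no confidence intervals for the regression.

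The scores are bounded (3. Data collection method). For gaming: "Total score ranges from 9 to 45, with a higher score indicating a higher level of gaming disorder". For pornography: "A total score ranges from 18-126, with higher levels indicating a higher level of porn addiction". PHQ-9 runs from 0 to 27, GAD-7 from 0 to 21, PSS-10 from 0 to 40 and the internet scale from 0 to 100. No skip for non-gamers or non-users of pornography is described. The Introduction cites 6% gaming addiction in one Egyptian university sample, 3.2% to 16.6% for pornography, and positive correlations of these behaviours with anxiety and depression.

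**The concern.** A large sample makes the slope estimate close to normal, but it does not make a constant-variance standard error correct. On a score with a hard minimum, respondents with low expected values are squeezed against the floor and vary little, while those with higher expected values vary more. If the respondents with extreme predictor values are also those with the larger residual variance, the default standard error understates the true spread of the slope, whatever the sample size.

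The gaming and pornography slopes are the likeliest to be affected, and the Rationale names these two behaviours as the gap in the literature. The analysis section already allows for non-normal data elsewhere (median and IQR, Mann-Whitney U) but carries no matching safeguard into the regression. At stake is the stated precision of those slopes.

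**Working it through.** **1. The plan's own figures.** The protocol gives no standard error, interval width or coverage for the regression, so there is none to reproduce. Its sample size does reproduce: 1.96² × 0.5 × 0.5 / 0.05² = 384.2, or 382.7 with a finite population of about 100,000 (assumed), hence 383. Then 383 × 1.10 = 421.3, rounded up to 422, and 422 × 11 countries = 4,642. With nonresponse as planned, about 383 × 11 = 4,213 are analysed.

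**2. Direction of the error.** For one predictor:
- default variance of the slope = mean(σᵢ²) / Σ(xᵢ − x̄)²
- true variance = Σ(xᵢ − x̄)²σᵢ² / [Σ(xᵢ − x̄)²]²

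The true variance is the larger one when σᵢ² is high where (xᵢ − x̄)² is high. With a right-skewed predictor the largest (xᵢ − x̄)² lie at high x. A positive association puts high outcome means there, and a floor in the outcome makes variance rise with the mean. All three conditions are needed.

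**3. From standard-error ratio to coverage.** If k = default SE / true SD, coverage ≈ 2Φ(1.96k) − 1.
- k = 0.97 (3% too small): 2Φ(1.901) − 1 = 94.3%
- k = 0.85 (15% too small): 2Φ(1.666) − 1 = 90.4%
- k = 0.75 (25% too small): 2Φ(1.470) − 1 = 85.8%

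**4. Simulation with three predictors.** All distributions are assumed. The underlying normal variables are correlated at 0.4. The internet score is symmetric, round(40 + 16u). The gaming score is round(14 + 8u) cut at 9, and the pornography score round(22 + 20u) cut at 18. That puts Φ((9.5 − 14)/8) = 29% and Φ((18.5 − 22)/20) = 43% at the minimum. The outcome is a rounded 0–27 score cut at 0. n = 4,220, with 1,200 replicates, so the Monte Carlo error of a coverage figure is about 0.6 to 1 point. Entries are internet / gaming / pornography; the robust column uses HC1.

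| Common slope | Outcome at 0 | Default SE / true SD | Default coverage, % | Robust coverage, % |
|---|---|---|---|---|
| 0.1 | 42% | 0.99 / 0.96 / 0.91 | 95.3 / 93.9 / 91.8 | 95.3 / 95.3 / 94.3 |
| 0.2 | 43% | 1.00 / 0.91 / 0.85 | 94.9 / 92.7 / 90.6 | 95.0 / 95.6 / 94.8 |
| 0.3 | 44% | 1.01 / 0.89 / 0.83 | 95.5 / 91.8 / 89.7 | 95.6 / 94.9 / 95.3 |
| 0.3 | 63% | 0.97 / 0.83 / 0.75 | 93.4 / 88.6 / 85.7 | 94.3 / 94.3 / 94.6 |
| 0.2 | 3% | 1.00 / 1.02 / 1.03 | 94.6 / 95.0 / 95.7 | 94.6 / 94.9 / 95.4 |
| −0.2 | 42% | 0.98 / 1.13 / 1.21 | 94.9 / 97.8 / 98.1 | 95.1 / 95.6 / 96.1 |

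These settings are heavy: only 1 − Φ((75.5 − 22)/20) = 0.4% reach the pornography cut-off of 76, below the cited 3.2% to 16.6%.

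**5. Milder three-predictor settings** (also assumed), gaming and pornography slopes:
- 15% of outcomes at 0, 6% at or above 76, score correlation 0.29, n = 4,642: default coverage 92% and 93%; HC3 94% and 96%.
- 23% to 38% at 0, 3% at or above 76, n = 4,642: default 90% to 92%; HC3 about 95%.
- 12% at 0, 3% to 8% at or above 76, correlations 0.16 to 0.31, n = 383 and 4,213: default about 91% to 95%; HC3 94% to 96%. The internet slope was nominal.

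With no association, default coverage was 94% to 96%. With a single floor-piled predictor, a positive association and 20% to 54% of outcomes at 0, it fell to 82% to 91%.

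**6. Effect on p<0.05.** With one predictor, t = r√[(n − 2)/(1 − r²)]. At n = 4,642, r = 0.11, 0.24 and 0.37 give t of about 7.5, 16.8 and 27.1. If the true SD were 25% larger, t would be 6.0, 13.5 and 21.7, all still significant. At r = 0.37 the standardised half-width would go from 0.027 to 0.033. With k = 0.85, only slopes with a default z between 1.96 and 1.96/0.85 = 2.31 change status. At n = 4,213, where one standard error is about 1/√4213 = 0.0154, that is r of about 0.030 to 0.036.

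**The case against.** The strongest objection is that the protocol does not fix what is criticised. It does not say that standard errors are model-based and promises no regression intervals, and a statistical analysis plan that is not shown may specify robust errors. This stands as a limit on priority. It does not remove the point, because the protocol names the method and the threshold, and the default of that method is the constant-variance error.

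The second objection is that every distribution is assumed. That also stands. A prevalence of addiction does not give the share of respondents scoring 18 or 9. The cited figures only make low, right-skewed scores plausible.

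The third is that little would change in practice. For significance calls this is largely right, as step 6 shows. What remains is overstated precision of real slopes.

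A reader might infer that default errors are too small whenever an association exists, so that everything under objective 3 under-covers. The documents do not support this, and the calculations contradict it. With a symmetric predictor and a censored-normal outcome, coverage was 94% to 96%. With almost no floor in the outcome it was about nominal. With a right-skewed predictor and a negative association, or a left-skewed predictor and a positive one, the default errors were too large.

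**Conclusion.** The concern holds in a limited form. If gaming and pornography scores are right-skewed with many respondents at the minimum, and are positively associated with depression and anxiety scores that themselves have a floor, the default standard errors for those slopes would be about 3% to 15% too small in realistic multi-predictor settings. Nominal 95% intervals would cover about 90% to 95%. Coverage falls below that only under heavier assumed floors, stronger slopes or a single-predictor model. The internet-addiction slope and null associations are largely unaffected.

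The result depends on assumed distributions, since the protocol reports no mean, SD, floor share or correlation for any score. It should not be read as a risk of widespread false positives: with no association the default errors are correct, and most p<0.05 conclusions would not change at the planned size. Low priority, but worth doing because robust errors correct the problem in whichever direction it runs.

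**What to change.** Keep the planned regression. Add one clause to Operational design, 4. Statistical analysis: standard errors, p-values and any confidence intervals from the linear regressions will be heteroscedasticity-robust (HC3).

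The model, the slope estimates and the sample size do not change. The cost is one clause and one software option. Intervals become slightly wider for some slopes, mainly gaming and pornography, and narrower where the default was too wide. In the settings above, robust errors gave about 93% to 96% coverage throughout; HC1 and HC3 differ negligibly with thousands of respondents.
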